Tax laws may require the Mount Sinai Finance Department to report the amount of payment you receive from Mount Sinai to the Internal Revenue Service (IRS) or other agencies as applicable. Generally, this reporting would take place if receiving payments that equal \$600 or more from Mount Sinai in a calendar year. You would be responsible for the payment of any tax that may be due.

9. Procedures - Narrative

Description of the Study Design

If you agree to participate in this research study, the following information describes what may be involved. All the research activities will take place at the MSMC.

The first step will be that the study nurse or doctor will explain you the basis for the study and all the research activities involved in your participation. Thereafter, you will be asked to sign this consent form. Before signing it, ask your study nurse or doctor anything that you do not fully understand. After you have signed this form, you will be asked some questions and will undergo some tests at the screening visit to see if you qualify and if it is safe for you to join the study.

All the procedures done during the study are solely for research purposes. The total volume blood collected during the 6-months of the study duration will be 75 mls. (5 table spoons). This amount is much less than one blood donation and, therefore, should not affect your health.

The procedures included in each one of the visits are described below:

Visit 1 Screening: This visit with last approx. 1 hour and it will take place at the 6th Floor of the Atran Building at the MSMC. We will ask you some questions about your medical history (about your health) and perform a physical exam that includes your weight, height, body temperature, blood pressure, pulse rate, and one EKG (checks the electrical activity of the heart). In addition, we will collect one sample of blood (1 table spoon) and urine to check for routine lab tests, hepatitis B and C, use of recreational drugs use (amphetamines, barbiturates, cocaine, opiates, cannabinoids, etc.) and HIV test. The results of the drug testing will NOT be placed in your medical record.

If you qualify and are willing to participate in the study, we will ask you to return for the 2nd visit within the next 30 days. In case you do not qualify, your participation will end in this visit.

Visit 2 Randomization: This visit will be approx. 4 hours long. You will be asked to report to the 6th Floor, Room 20 of the Atran Building at the MSMC in fasting state. This visit will serve to perform all the baseline (pre-treatment) procedures. The procedures to be performed during this visit will be:

- Magnetic Resonance Imaging to study cardiac parameters of your cardiac function. You will be introduced inside of a magnet where you should stay as quiet as possible for about 45-60 minutes. As routinely done in clinical you will receive Gadolinium that is a contrast that facilitate the visualization of your heart. This procedure does not involve the exposure to any ionizing radiation and thus, does not present any important risk to your health.
- Oxygen consumption. You will be asked to walk on a treadmill while being EKG-monitored. Your blood pressure will be monitored before and after the procedure. You will also wear a mask that will allow to measure the Oxygen consumption. This procedure will take approx. 20-30 minutes
- 6-minute walking test. - We will ask you to walk for a total of 6-minutes and then walked distance will be recorded. If necessary you will be allowed to stop and rest during the 6-minutes period. This walk will be repeated at the end of the 6-months of the study duration and the difference between the distance walked in the two procedures will tell us about the effects of the treatment.
- Heart Failure Questionnaire. - we will ask you some questions about the quality of life. The questioner will be repeated at the end of the 6-months of study.
- We will collect one blood sample (15ml 1 stable spoon) to study some blood parameters

Following baseline testing procedures, you will be randomized to one of two possible treatment groups (Empagliflozin or Placebo). Randomization is a process used in clinical studies to make sure that the observed effects of study treatment are real. The study treatment you get will be chosen by chance, like flipping a coin.

Neither you nor the study doctor will choose what study treatment you get. You will have an equal chance of being assigned to either study treatment group. One group will receive a pill of empagliflozin (10mg/day) while the other (placebo-control) group will receive a sugar pill without active medicine. The study pills will be taken orally and preferably at the same time every day. The study pill will be taken in addition to all the drugs prescribed by your physician. You will be provided detailed instructions on how to take your study pills in person during this visit.

The treatments in this study will be 'blinded', meaning neither you nor the study investigators will know which study treatment you are getting. This information could be obtained in an emergency however, you will not be told which study treatment you are getting, but your study doctor will know.

At the end of this visit, we will provide you with a supply of the assigned pills and you will be allowed to go home. We will schedule your next visit within 1-2 weeks of visit 2.

Visit 3 Safety: This visit will last approx. 1 hour. You will be asked to report to the 6th Floor of the Atran Building at the MSMC in a fasting state. During this visit, we will perform the same procedures as per the visit 1. The most important reason for this visit is to monitor the safety and efficacy of the medicine that you are taking. During this visit, we will record your vital signs (weight, height, body temperature, blood pressure, pulse) and collect one blood sample (15mls or 1 table spoon) for routine lab test (lipids, glucose, liver enzymes, etc.). We will ask you questions about your health since your last visit. Thereafter, we will provide you with a supply of the assigned pills and your visit will end.

Visit 4 Maintenance: This visit will last approx. 1 hour. Within 12-14 weeks of the previous visit, you will be asked to report to the 6th Floor of the MSMC in a fasting state. The reason for this visit is to continue monitoring the safety and efficacy of the medicine that you are taking. We will repeat the procedures done during your previous visit (i.e. record your vital signs and collect one blood sample for routine lab test) and ask you questions about your health status since your last visit. Thereafter, we will provide you with a supply of the assigned pills and your visit will end.

Visit 5 Final: This will be the last visit and will have an approx. duration of approx. 4 hours. You will be asked to report to the 6th Floor of the Atran Building at the MSMC in a fasting state. During this visit, we will repeat the procedures performed during visit 2. The procedures will be: Magnetic resonance imaging, Oxygen consumption, 6-minute walking test, the Minnesota questioner and collect one blood sample (15 mls or 1 table spoon). We will record your vital signs (body weight, height, body temperature, blood pressure, pulse) and EKG to check your health status. The comparison of the results obtained during visit 2 and visit 5 will allow us to delineate the effects of the study drug. At the end of this visit, your participation in the study will end.

Description of Procedures Being Performed

Cardiac Magnetic Resonance Imaging (CMR): CMR studies will be performed at the Cardiac Imaging Facilities of the Mount Sinai Heart under the direction of [name] (Investigator of the proposal). Images will be acquired with a 3.0 Tesla magnet (Achieva, Philips Medical Systems, Netherlands). Steady-state free precession short axis images (TR 3.6 ms, TE 1.6 ms, flip angle 45°, field of view 250 x 250 mm, SENSE factor 3, voxel size 1 x 1 x 5 mm, no gap, number of averages 3, bandwidth 1286 Hz, 12 lines per segment) from the LV base through LV apex will be used for the quantification of LV volumes, ejection fraction and mass. Late gadolinium enhancement (LGE) will be performed 15 minutes after the administration of gadolinium (Magnevist, 0.2 mmol/kg) using an inversion-recovery fast gradient echo sequence (TR 9 ms, TE 5.4 ms, TI optimized to null normal myocardium, gating factor 3, field-of-view 250 x 250 mm, pixel size 1 x 1 x 5 mm, SENSE factor 3, number of averages 3, bandwidth 232 Hz, TFE factor 16). A Look-Locker sequence will be performed before and 10 minutes after gadolinium administration to evaluate interstitial myocardial fibrosis using the T1 mapping technique. All CMR images will be blindly analyzed using commercially available software (Extended MR Workspace, Philips Medical Systems, Netherlands). Epicardial and endocardial

contours will be traced in each SSFP cine image to obtain LV end-diastolic volume (LVEDV), LV end-systolic volume (LVESV), LV ejection fraction (LVEF) and LV mass; by convention, papillary muscles will be included in the LV cavity. LV scar size will be measured by LGE and expressed as a percentage of the LV mass; the absolute MI size also was quantified in grams (calculated as volume multiplied by myocardial density [1.05 g/cm³]). Infarct was defined as myocardium with signal intensity was higher than 3 standard deviations of that in remote, normal. Longitudinal relaxation times for T1 mapping quantification will be measured using cvi42 software (already present in our clinical facility).

Peak Oxygen Consumption: Cardiopulmonary exercise testing will be done prior to randomization and at 6 months of therapy. Patients will report in the fasting state to the Mount Sinai Research Cardiopulmonary Exercise laboratory on Guggenheim 6. This facility is under the direction of [name] (investigator of this proposal). Patients will perform a treadmill exercise using the modified Naughton protocol with continuous EKG monitoring. Blood pressure will be measured prior to exercise, at the end of each exercise stage and at peak exercise. The patient will be connected using a mouthpiece to a metabolic cart (Medical Graphics Ultima Cardio 2, St Paul, Minn) for continuous measurement of oxygen consumption, carbon dioxide production and minute ventilation. Symptom limited exercise will be performed. Perceived levels of dyspnea and fatigue will be measured using the Borg scale. Peak VO₂, VE/ VCO₂ ratio and the aerobic threshold will be recorded.

6 minute walk test: Patients will perform a 6 min walk test prior to and 6 months post randomization. In a quiet 100 ft hall the patients will be instructed to walk as fast and perform as many laps as possible between the distance markers over a period of 6 minutes. The walk test will be supervised but unencouraged. Blood pressure and heart rate are measured at the start and end of the 6 min. Patients will be allowed to stop and rest if needed. The total distance walk will be recorded.

Heart Failure Questionnaire: We will ask you some questions about the quality of life. The questionnaire will be repeated at the end of the 6-months of study.

Inflammatory and cardiovascular biomarkers: will be assessed two times throughout the study: at the time of randomization and at the end of the study using the Human Cytokine/Chemokine Panel I kit (Luminex; Cat # HCYTMAG-60K-PX41) that allows to measure 41 inflammatory cytokines and chemokines with well-established predictive value for CV risk and mortality. The effect of the treatment will be assessed by changes in the value of the selected biomarkers between the randomization and the end of study time–points.

Description of the Source Records that Will Be Used to Collect Data About Subjects

All the data will be recorded in a specifically prepared Case Report Form (CRF) that includes all the parameters mentioned in the next section

Description of Data that Will Be Collected Including Long-Term Follow-Up

The major end-points are the effect of the treatment on cardiac function assessed by CMRI. Vital signs and routine blood parameters will be assessed at each visit. In addition at the screening and at the end of the 6-months of follow-up we will monitor the effect of the treatments on systemic cytokines and chemokines with well-established predictive value for CV risk and mortality by using the Human Cytokine/Chemokine Panel I kit (Luminex; Cat # HCYTMAG-60K-PX41).

10. Procedures - Details

Surveys or Interviews

Yes

Names of Standardized Instruments

To determine if there is a change in the patient-reported quality of life by the Minnesota Living with HF and SF-36 questionnaires. We will also ask for any adverse event at each of the visits.

11. **Consent - Obtaining Consent**

Consent Process

Adult Consent

Where and When Consent Will Be Obtained

Informed consent form will be obtained at the Heart Failure Unit and/or Atran 6th Floor Room 20

Waiting Period for Obtaining Consent

A maximum 4 weeks

SOP HRP-090 Informed Consent Process for Research Is Being Used

Yes

Process to Document Consent in Writing

Will Use Standard Template

Non-English Speaking Participants Will Be Enrolled

Yes

What Languages Other Than English Will Be Used

Spanish speaking participants will be also approached. They will be offered a consent form in Spanish.

What Process Will Be Used

Long Form

12. **Data – Collection, HIPAA and Storage**

Description of Health Information That Will Be Viewed, Recorded, or Generated

- Clinical History
- Vital signs
- Routine clinical lab tests
- Cardiac function assessed by CMRI
- Oxygen consumption
- Systemic biomarkers

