effects associated with empagliflozin administration, we are proposing to conduct a pilot randomized, double blind, placebo- control, single-center study to investigate the postulated "cardiovascular" benefits of empagliflozin 10mg/day vs placebo involving non-diabetic HF patients with reduced ejection fraction.

Primary Endpoints

The primary end-point will be to determine whether empagliflozin mitigates changes in LV end systolic volume (ESV) or LV end diastolic volume (EDV) in HF patients without diabetes when compared to placebo. We have chosen LV volume because it is the strongest predictor of adverse cardiovascular outcomes even after adjusting for LVEF and MI size (White HD *Circulation*. 1987;76:44–51 and Migrino RQ *Circulation*. 1997;96:116–121).

Secondary End-points

1. To determine changes in LV mass, LV-EF and remodeling index (LV mass/LV-EDV) with empagliflozin compared with placebo.
2. To determine if there is a change in left atrial volume (an accurate indicator of chronic increase in LV filling pressures) with empagliflozin compared with placebo.
3. To determine if there is a change in right ventricular (RV) EDV, RV-ESV and, RV-EF with empagliflozin compared with placebo.
4. To determine if there is a change in cardiac interstitial fibrosis as assessed by T1 mapping with empagliflozin compared with placebo.
5. To determine if there is a change in VO₂ Oxygen consumption with empagliflozin compared with placebo.
6. To determine if there is a change in Visceral and epicardial fat as measured by CMRI with empagliflozin compared with placebo.
7. To determine if there is a change in arterial stiffness measured by CMRI with empagliflozin compared with placebo.
8. To determine if there is a change in body composition analysis (BCA anthropomorphic measurements) with empagliflozin compared with placebo.
9. Effect of the treatment on several cardiovascular and inflammatory biomarkers with empagliflozin compared with placebo.
10. To determine if there is a change in exercise tolerance by the 6 min walk test with empagliflozin compared with placebo.
11. To determine if there is a change in the patient-reported quality of life by the Minnesota Living with HF and SF-36 questionnaires.

Safety and Tolerability

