All approached participants will have a diagnosis of HF. Upon signing of the informed consent form, a blood sample will be collected and analyzed to assure that participants fulfill ALL the inclusion criteria but NONE of the exclusion criteria. We will ask questions about their medical history and perform a physical exam that includes weight, height, body temperature, blood pressure, pulse rate, and EKG. In addition, we will collect blood and urine to check for routine lab tests, hepatitis B and C, use of recreational drugs and HIV test. The results of the drug testing will NOT be placed in the participant's medical record.

8. Subjects - Risk and Benefits

Risks to Subjects

Empagliflozin is approved by the FDA for the treatment of high levels of glucose in diabetic subjects. This drug has been studied in tens of thousands of patients and, despite its well-established benefits, the adverse effects observed and that could very rarely affect you are:

- Low sugar levels manifested as blurry vision, accelerated cardiac pulse, irritability, nervousness, headaches, shivers, sweating, tireless, tingles and/or appetite loss.
- Blood pressure lowering manifested as headache, dizziness, confusion, irritability, sweat and irregular cardiac pulse.
- Dehydration manifested as headache, dizziness, confusion, weakness specially when standing up.
- Ketoacidosis manifested as headache, fatigue, nausea/vomiting, stomach ache, breathing difficulties, abdominal pain, urinating urges, appetite loss.
- Urinary infections (penis in men and vagina in women) manifested as frequent urination urges, irritation while urinating, blood and/or bad smell of the urine, pain in the stomach and/or pelvis.
- Allergies manifested as cutaneous rushes, inflammation and/or itching in the face, tongue and throat as well as dizziness and breathing difficulties.
- In case you experience any of these symptoms, stop taking the study drug and immediately contact the investigators at the phone number provided below in this document.

- There are no reports of any psychological or social risks associated with the treatment.
- The risks of a blood draw include pain, bruising, and the slight possibility of infection at the place where the needle goes in. Some people feel dizzy or may faint during or after a blood draw.

Description of Procedures Taken to Lessen the Probability or Magnitude of Risks

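### Secondary endpoint 4 takes interstitial fibrosis from T1 relaxation times with no same-day haematocrit specified, so a one-arm change in haematocrit could be misread as a change in fibrosis

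*Combined protocol and SAP*

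**What the plan says.** Section 2 (Secondary End-points, item 4) sets the aim: "To determine if there is a change in cardiac interstitial fibrosis as assessed by T1 mapping with empagliflozin compared with placebo". It does not say which T1-derived quantity represents fibrosis.

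Section 9 (Description of Procedures Being Performed, Cardiac Magnetic Resonance Imaging) gives the acquisition: "A Look-Locker sequence will be performed before and 10 minutes after gadolinium administration to evaluate interstitial myocardial fibrosis using the T1 mapping technique". The read-out follows in the same section: "Longitudinal relaxation times for T1 mapping quantification will be measured using cvi42 software". The text available names no blood-pool T1, partition coefficient, ECV or haematocrit. The data analysis plan in Section 12 has no adjustment specific to this endpoint.

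Blood is drawn at both imaging visits, but the analytes are left open. For Visit 2 the plan says "We will collect one blood sample (15ml 1 stable spoon) to study some blood parameters"; for Visit 5 it lists none. Section 9 also promises routine blood parameters at every visit. Where it itemises routine tests, at Visit 3, it names lipids, glucose and liver enzymes and leaves the list open.

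On the drug, Section 2 (Background) says the class acts on urinary glucose excretion. Section 8 (Risks to Subjects) includes "Dehydration manifested as headache, dizziness, confusion, weakness specially when standing up", in a list introduced by "the adverse effects observed and that could very rarely affect you are".

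**The concern.** A relaxation time is not itself a measure of fibrosis. Post-contrast myocardial T1 depends on how much gadolinium remains in plasma at 10 minutes, and so on renal clearance and plasma volume as well as on the interstitial space. The partition coefficient divides by the blood signal. That largely removes the gadolinium level, so far as 10 minutes approximates equilibrium, but leaves haematocrit in the result.

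Randomisation balances haematocrit at baseline. It does not balance a change that treatment causes. If the active drug concentrates the blood, the artefact falls in one arm, and blinded image reading does not remove it. A rise in haematocrit looks like more fibrosis, so the likelier damage is a masked benefit or an apparent harm.

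The gap is also hard to repair afterwards. The images will exist, but a haematocrit not measured near the scan cannot be recovered, and a screening value may be up to 30 days before Visit 2. With the metric left open, several different fibrosis results could be produced from the same images.

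**Working it through.** The plan gives no T1 value, ECV, haematocrit, SD or power for this endpoint, so there is no figure of its own to reproduce.

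**Inputs from the documents.** 80 completers (Section 4) with equal allocation (Section 9), taken as 40 per arm; significance at P<0.05 (Section 12), taken as two-sided.

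**Assumed inputs.** Baseline haematocrit (Hct) 0.40; true ECV 0.30 and unchanged; a mean Hct rise of 1, 2, 3 or 5 points in the active arm only; SD of change in the metric 5%, 10% or 15% of baseline.

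**Step 1: the relation.** Partition coefficient λ = (change in 1/T1 of myocardium) / (change in 1/T1 of blood) = ECV / (1 − Hct). With ECV fixed, the relative change in λ is (1 − Hct at baseline) / (1 − Hct at follow-up) − 1, which does not depend on the ECV chosen.

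**Step 2: size of the artefact.** Baseline λ = 0.30/0.60 = 0.500.

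| Hct rise | Ratio | λ | Relative change |
|---|---|---|---|
| 1 point | 0.60/0.59 | 0.508 | +1.7% |
| 2 points | 0.60/0.58 | 0.517 | +3.4% |
| 3 points | 0.60/0.57 | 0.526 | +5.3% |
| 5 points | 0.60/0.55 | 0.545 | +9.1% |

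Baseline Hct matters little: for a 3-point rise the change is +5.1% from 0.38 and +5.5% from 0.42.

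**Step 3: what that would do to the test.** With no true fibrosis effect, let z = relative change / (SD × √(2/40)). The chance of P<0.05 is Φ(z − 1.96) + Φ(−z − 1.96). Example: a 3-point rise with SD 10% gives z = 0.0526/(0.10 × 0.2236) = 2.35 and a chance of 65%.

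| Hct rise | SD 5% | SD 10% | SD 15% |
|---|---|---|---|
| 1 point | 33% | 12% | 8% |
| 2 points | 87% | 34% | 18% |
| 3 points | 99.7% | 65% | 35% |

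The nominal rate is 5%. Nearly all of these rejections would point to more fibrosis on the drug.

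**Step 4: with the correction.** ECV = (1 − Hct) × λ. After a 3-point rise, 0.57 × 0.5263 = 0.300, the true value. The artefact is zero for every assumed rise.

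**Step 5: post-contrast T1 alone.** Assume native T1 of 1200 ms and post-contrast T1 of 450 ms. Then 1/T1 post-contrast = 1/1200 + (1/450 − 1/1200) × (1 + s), where s is the relative rise in plasma gadolinium. For s = 1%, 3% and 5%, T1 falls to 447, 442 and 436 ms. The documents give nothing from which to set s, and slower or faster clearance would change its size and sign. Native T1 involves no gadolinium and is not covered by any of these figures.

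**The case against.** The strongest reply is that the plan is silent on the correction and does not reject it. Measuring relaxation times in software need not be the last step: pre- and post-contrast T1 are what ECV requires, and blood is drawn at both imaging visits. This stands in part. ECV remains feasible, and a reader should not infer that the investigators decided against it. But the plan secures neither the metric nor the haematocrit on which that defence depends.

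A reader might also infer that the drug would shift this endpoint in one arm. The documents do not support that. They state no haematocrit effect and no change in gadolinium clearance, and they call the listed risks very rare. One affected participant among 40, with a 5-point rise, would move the arm mean of λ by only 9.1%/40 = 0.23%. The tabulated shifts need a mean change across the whole arm. Section 2 does list blood pressure lowering as a class effect, but that is not haemoconcentration, and the same section reports no major blood pressure difference in the earlier outcome trial. So the word is could. The very-rare wording introduces symptomatic adverse effects, however, and does not rule out a small average change.

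Two further limits stand. The percentages apply to the uncorrected partition coefficient, which the plan does not name, and should not be read as shifts in relaxation times. And this is not one of only a few structural measures: LV mass, remodeling index, left atrial volume, RV volumes and epicardial fat are also secondary endpoints.

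**Conclusion.** The point holds as a possible bias in one of 11 secondary endpoints of a pilot trial. As written, the fibrosis claim rests on a read-out that can move with haematocrit and gadolinium clearance, and nothing in the plan separates those from fibrosis.

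The size is conditional. If the uncorrected partition coefficient were used and mean haematocrit rose in one arm by 1 to 5 points from 40%, the metric would rise by 1.7% to 9.1% with no change in true ECV. Whether that matters depends on an SD the plan does not give: a 1-point rise takes the 5% error rate to between 8% and 33%, and a 3-point rise to between 35% and 99.7%. Every haematocrit shift and SD here is an assumption. For post-contrast T1 the direction also depends on clearance.

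A reader might infer that scar measured by late enhancement adds to the arm difference. The plan does not define the T1 region, so scar could be mixed into an interstitial measure. That would mainly dilute the endpoint, and no arm-specific bias is shown.

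The change is worth making because it is cheap and the missing measurement cannot be obtained later.

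**What to change.** Define secondary endpoint 4 as the change from Visit 2 to Visit 5 in ECV = (1 − haematocrit) × (change in 1/T1 of myocardium / change in 1/T1 of blood). Use the pre-contrast and 10-minute post-contrast T1 scans already planned, with a haematocrit measured on the blood already drawn on the day of each scan. State the formula in Section 9 and name haematocrit among the Visit 2 and Visit 5 analytes. Report relaxation times as supportive only.

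As a secondary step, define the T1 region and keep out myocardium above the plan's own late-enhancement threshold of 3 SD over remote myocardium, so that the measure reflects interstitial fibrosis.

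The cost is one added assay at each imaging visit and a blood-pool contour on images already acquired, with no extra scan or visit. The downside is that participants without a same-day haematocrit drop out of this one secondary endpoint; their number should be reported by arm.
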